For Task 2, graded mixed nerve injury recovery will also be evaluated. For partial transections, a 3-D printed nerve cutting guide will allow graded transections of 25%, 50%, and 75%. Controls of 0% and 100% mixed nerve crush or cut injury will be from Task 1. Again, we will use 12 rats per group, sacrificed on 4 separate dates, for a total of 48 rats per group (= 3 graded transections * 48 = 144 total additional rats).

For Task 3, two additional groups will be added: autograft and conduit repair. Again, we will include 12 rats per group, sacrificed on 4 separate dates, for a total of 48 rats per group (= 2 different repairs * 48 = 96 additional rats).

For all Tasks, a total of 576 rats will be required.

Aim 2: Determine if DTI fiber tracking can predict recovery of peripheral nerve function in human case studies (crush or cut with repair). Pure sensory, motor, and mixed nerves will be evaluated.

Using the studies from Aim 1 as model of failed nerve recovery, human *in vivo* MRI case studies will be performed. DTI data will be collected at 1, 3, 6, and 12 months after injury and surgical repair. The first time

point was chosen to allow for inflammation to subside, which can confound DTI-based estimates of nerve regeneration (edema can result in increased diffusivities that can be incorrectly interpreted as changes in myelination and/or axonal integrity⁶³). We expect that changes due to degeneration/regeneration will be detectable via DTI at this time, as previous case studies noted detectable differences as early as 1 month^{50,51} (as well as our preliminary data in Figs. 11,12). The final time point of 12 months was chosen to allow adequate time for nerve regeneration. This will yield a ground truth assessment of the success of the repair at the end of the study. DTI results will be correlated with results from nerve conduction and EMG studies if clinically indicated acquired at the 3-, 6- and 12-months after surgery. **We hypothesize that DTI will be able to stratify patients that are recovering versus patients with failed repair at earlier times points than nerve conduction and EMG.** An outline of the study is shown in Figure 13.

[figure not shown]

FIG 13. Study design timeline following surgical repair. MRI will be performed at 1, 3, 6, and 12 months after surgery to estimate DTI parameters. NCS/EMG data will be collected for comparison at 3, 6, and 12 months.

Patient Population

Based on designs from previous clinical trials that assessed nerve function, we plan to enroll patients with Sunderland Class V (transection) injuries of injury that will undergo nerve repair. Additional patients with pure motor or sensory injuries will also be investigated. In all patients, complete nerve transection will be verified at the time of the surgery. Upper extremity injuries from the mid-forearm and distal will be eligible. This patient population is considered optimal due to the frequency of occurrence of extremity nerve injuries, the seriousness of the impairment when there is an insensate finger and or lack of intrinsic hand muscle function, and the availability of objective computerized mechanisms to assess outcome.

Inclusion criteria: We will consider subjects between 18 and 64 years old that are diagnosed with a Sunderland Class 5 traumatic neuropathy (transection injury) of upper extremity nerves that require repair. We plan to enroll only patients that have the preceding injury that are deemed candidates for immediate operative repair of this injury and do not have significant medical comorbidities precluding immediate operative intervention. Additionally, patients must be willing to comply with all aspects of the treatment (post-operative visits, occupational therapy) and evaluation schedule over the following 12 months. We plan to include subjects who have peripheral nerve injuries that are complicated by significant vascular or orthopedic damage.

Exclusion criteria: Patients will be excluded from enrollment if their injuries exhibit gross contamination, in circumstances where soft tissue coverage is inadequate, or when staged repair is planned. We will also exclude patients that are diabetic, have been diagnosed with a neuromuscular disease, or are undergoing chemotherapy, radiation therapy, or other treatments known to affect the growth of the neural and vascular system. We will exclude all patients currently enrolled in another investigational study or those who are unlikely to complete the normal regime of occupational therapy. For safety reasons, all pregnant women or women who are breast-feeding will also be excluded from this study along with subject with any ferromagnetic objects that cannot be removed (cardiac pacemakers, aneurysm clip, etc.), and/or a history of claustrophobia. All subjects will undergo a standardized MRI metal screening prior to each MRI scan, and signed consent will be obtained prior to all examinations.

Sample size: Previous optimization DTI studies in human median nerves reported mean (\pm SD) FA values of 0.7 ± 0.04 ⁴². We do not have human longitudinal data from which we can estimate an effect size; however, Takagi et al.²² performed ex vivo DTI in a rat injury model longitudinally and reported mean FA values of 0.5 following trauma (FA values are preserved across fixed and in vivo tissue⁶⁴). We, therefore, assume a similar mean FA value after surgery (0.5) with a SD taken from the aforementioned human optimization study (0.04) for our power analysis below. A conservative goal is to detect a 10% increase in FA from this decreased value to stratify successful from unsuccessful surgical interventions. If we test for

differences between these cohorts via a two-tailed pooled Student's t-test ($p = 0.05$), 24 patients would yield a study power of 0.8. Thus, assuming a failure rate of 40%, we will scan 24 patients, approximately 14 of which should have successful surgeries and 10 of which should have unsuccessful surgeries.

Subject recruitment: Patients will be recruited through consultations to the hand service at VUMC. Patients scheduled to receive nerve repair procedures meeting the criteria will be considered for participation. All patients must give informed consent prior to any study procedures. In the case of patients who are not competent to make a decision regarding study participation, they will be excluded from the study. A copy of the signed study consent document and authorization forms will be given to each patient. All signed consent documents will be stored in a locked cabinet in the office of the research coordinator or Principal Investigator, [name]. In an average year, the Vanderbilt Medical Group performed over 372 digital nerve repairs and an additional 50 repairs involving mixed nerve loss in the upper extremity. As a result, we anticipate reaching our target recruitment of 24 mixed injury subjects within approximately 18 months, leaving adequate time for sequence development in the early stages of the award (1st six months) and 12-month follow-up scan in the latter stages of the award (3rd year). It is rare to see a pure motor nerve injury (ulnar motor branch of the hand). These ulnar motor branch injuries will be additionally included through the duration of the study, but it is unlikely that more than 10 will be observed in a single center study.

Investigational Procedure

After inclusion criteria are met, a standard peri-operative anesthesia evaluation will be undertaken. If the patient is deemed to be of appropriate operative risk to undergo immediate operative repair, informed consent will be obtained and patients will be enrolled in the study. These determinations and obtainment of informed consent will be by research coordinator or principal investigator. It is anticipated that patients will be enrolled primarily through the emergency and trauma units. Clinical testing will occur as scheduled in Table 1. EMG/NCS will be performed after injury if clinically indicated, and at 1,3,6, and possibly 12 months after injury. These studies will be limited to focus on the injured nerve to decrease exam time and discomfort. If patients have fully recovered clinically, additional EMG's will not be performed.

No surgical details will deviate from the current standards for operative repair. All wounds will be closed in the fashion deemed appropriate by the operating surgeon. In essence, the only deviation from the expected surgical repair of these injuries will be post-operative monitoring after nerve repair.

Follow Up: Postoperatively, we plan to follow each patient for a total duration of 12 months after repair, anticipating follow up at 1 week, 1 month, 3 months, 6 months, and 12 months post injury. The data to be collected at each visit are shown in **Table 1**.

DTI Acquisitions

Both arms will be scanned in each subject, with data from the uninjured arm serving as an internal control in each patient. Participants will be imaged in the prone position with the arm being imaged extended over the head. Upon completion of the MRI protocol in the 1st arm, participants will be repositioned with the other arm above the head; and the same MRI protocol will be performed in the 2nd arm. To minimize discomfort, the total protocol duration (DTI scans plus additional calibration scans, scout images, T₁-weighted anatomical, and T₂-weighted anatomical protocols) will be less than 30 minutes for each arm.

Human MRI studies will be performed on our 3.0-Tesla Philips Achieva whole-body MR scanner (Philips Healthcare, Best, The Netherlands). A two-channel body coil will be used for excitation, while a multi-element extremity coil will be used for signal reception. We currently have an array of multi-element coils that allow us to perform studies of both distal nerves of the arm. The details of the DTI protocol will be informed from the animal studies and will be optimized during the initial phase (6 months) of this study in healthy subjects. As a starting point, we will rely on previous DTI optimization studies in human median nerve ⁴⁴, which employed a multi-slice diffusion-weighted spin-echo sequence with the following parameters: number of diffusion directions = 15, $b = 1000 \text{ s/mm}^2$, TR/TE = 8000/52 ms, in-plane resolution = 1.0 x 1.0 mm², field-of-view = 80 x 80 mm², number of slices = 25, slice thickness = 4 mm, numbers of signal averages = 4, SENSE acceleration factor = 2, and SPAIR fat suppression. Using this protocol, DTI data can be acquired in approximately 10 minutes, leaving adequate time to complete the entire protocol for each arm within 30 minutes.

Table 1. Demographics and Outcome Variables and follow up for nerve injury patients.

Data Recorded	Study Entry	Postoperative Day				
		1	30	90	180	360
Demographics						
Age	X					
Sex	X					
Race	X					
Medical Comorbidities	X					
Surgical History	X					
Social History	X					
Worker's Compensation Status	X					
Occupation	X					
Concurrent Injuries	X					
Laboratory Values	X					
Rehabilitation Regimen		X	X	X	X	
Affected Limb Physical Examination	X	X	X	X	X	
Normal Limb Physical Examination	X		X	X	X	
Distance from Injury to Finger Tip	X					
Outcome Variables						
Pain Assessment	X	X	X	X	X	
Medical Research Council Classification	X	X	X	X	X	
Data Recorded	Study Entry					
Outcome Variables Continued						
Static 2-Point Discrimination	X	X	X	X	X	
Moving 2-Point Discrimination	X	X	X	X	X	
Michigan Hand Questionnaire	X	X	X	X	X	
Grip Strength	M	M	M	M	M	
Nine hole peg test		M	M	M	M	
Short Form 12	X	X	X	X	X	
Dash Questionnaire	X	X	X	X	X	
Complications		X	X	X	X	
MRI			X	X	X	

X = ALL COHORTS, M= MIXED NERVE

DTI Analysis

In each subject, we will acquire 15 diffusion-weighted (DW) volumes, each sensitized to diffusion along a different direction, along with a non-DW volume as described above. All DTI pre-processing and tensor estimations will be performed via FMRIB's Software Library (FSL)⁶⁹. All volumes will first be coregistered to the non-DW volume using a 3D affine transformation to correct for the effects of motion and eddy currents. If rotations to the data are applied, the gradient table will be rotated accordingly. Then, the diffusion tensor **D** will be calculated using a weighted linear least squares approach. Three eigenvalues and corresponding eigenvectors will be calculated from **D**, defining the diffusivities and principal direction of diffusion, respectively. From this, we will calculate the FA, MD, RD, and AD on a voxel-wise basis. As a reminder, MD represents the mean diffusivity across all directions, AD represents diffusivity parallel to the principal directions of the axons, RD represents diffusivity parallel to the principal directions of the axons, and FA quantifies the degree of diffusion anisotropy. During regeneration, we expect to observe an increase in FA and decrease in MD due an increase in the order and total number of diffusion barriers, respectively. The relative impact of RD and AD on these changes has yet to be established; however, it has been suggested that RD primarily reflects myelination, while AD primarily reflects axonal degeneration/regeneration^{22, 53}.

The eigenvalues/eigenvectors estimated from **D** will also be used to perform fiber tractography, which will be performed using the ExploreDTI toolbox⁷⁰. Seed regions-of-interest (ROIs) of each nerve will be drawn

in the most proximal slice to seed each fiber tract. FA threshold values and the angulation tolerances determine the limits for the automatic tracking of fibers. Previous work⁴³ has determined optimal reconstruction parameters for fiber tractography of healthy nerves (FA threshold = 0.2 and maximum angulation tolerance = 10). We will use these parameters as a starting point, noting that adjustments may need to be made in regenerating nerve. Tractography results will be quantified by estimating the mean length of fiber tracts as well as the relative number of fiber tracts that successfully reach ROIs defined in the most distal slice. During regeneration, we expect mean fiber lengths and relative tract numbers to increase.

Statistics

Statistical analyses will be performed using STATA/IC 13.1 (StataCorp, College Station, TX). In controls, tests will be performed to evaluate i) the relationship between DTI metrics and confounding variables (age, sex, and BMI), ii) the variability of DTI metrics between nerves and along nerve segments and iii) the repeatability of DTI metrics across scans and raters. In patients, tests will be performed to i) evaluate the ability of DTI to predict failed nerve recoveries at each time point (using evaluations at 12 months as the ground truth) and ii) evaluate correlations between the DTI parameters and EMG/NCS results.

We will first examine the potential confounding influence of BMI, age, and sex on each DTI parameter via multiple linear regression in controls. A Shapiro-Wilk test on the regression residuals will be used to test for normality. For the sake of this proposal, we assume normality and that parametric statistical tests are appropriate. We will employ corresponding non-parametric tests if normality is not observed. The effects of BMI, age, and sex on DTI parameters will be quantified via Pearson partial correlation coefficients. To test for variations across nerve and along nerve segments in control subjects, an ANOVA will be performed. If significant variation is observed, post hoc pair-wise comparisons will be performed using a Bonferroni multiple comparison test.

To understand the ability of DTI parameters to provide estimates of nerve regeneration, it is important to first understand the reliability of the acquisition (interscan) and assessment (interrater) methodology. To estimate the interscan reliability, intraclass correlation coefficients (ICC) will be calculated for each DTI metric in the control scan-rescan data. To test for changes in DTI parameters across time, paired t-tests will also be performed between each timepoint. Finally, the interscan variabilities of DTI parameters will be estimated via the repeatability coefficient (RC), which is defined as 1.96 times the SD of the mean difference between scans. Analogous analyses will be performed for the inter-rater data, where nerve ROIs will be independently defined in 12 control subjects by two trained raters.

Patients will be grouped into “failed” or “successful” cohorts based upon our evaluations at 12 months. All tests below will be performed in three nerve segments of the injured nerve: i) proximal to the injury, ii) at the injury site, and iii) distal to the injury. The percent difference in DTI parameters between injured and non-injured arms will be used in all analyses to control for confounding factors (e.g., age). To evaluate the ability of DTI to predict failed nerve recoveries at each time point, we will perform two sets of test. First, significant difference between “failed” or “successful” groups will be tested (at each time point and nerve segment) via a Bonferroni multiple comparison test. Second, and ROC analysis will be performed to evaluate the diagnostic potential of each normalized DTI parameter at each time point and nerve segment. Finally, to evaluate relationships between DTI parameters and NCS/EMG data (e.g., CMAP), pairwise Pearson correlations and Bonferroni corrected significance values will be calculated.

Potential Pitfalls/Solutions

As previously mentioned, we expect to be able to meet our subject recruitment targets (24 subjects) within the first two years of the award, allowing one additional year for follow-ups. If we encounter recruitment (or retention) issues, we will investigate the feasibility of performing DTI in the digital nerves of the hand, as injury to these nerves is much more common. Our preliminary studies indicate that our DTI protocols have sufficient resolution to robustly perform DTI of the nerves at the level of the wrist. Performing tractography from these larger, more proximal nerves (median and ulnar) to the more distal digital nerves of the hand may also be feasible, and will be investigated if recruitment and/or retention issues are encountered.

In interpreting our DTI results in patients, it is important to consider each DTI metric’s specificity to different pathological processes. Although diffusion metrics are primarily sensitive to axonal integrity, studies

have shown the DTI indices are also sensitive to myelination and inflammation^{63, 65}. Given that all of the processes may occur concurrently during nerve degeneration/regeneration, a direct linkage between changes in DTI parameters and nerve recovery may be difficult, especially at the earlier time points when some level of inflammation may be present. Although histological evaluation of these various processes is not feasible in humans, we have a number of validated quantitative measures (EMG, NCS) that, when available, can be used to validate our DTI findings in humans. In addition, we will rely on the proposed validation studies in animal models (Aim I) to better understand the relationship between our DTI observations and underlying pathology.

In addition to interpretation issues, the sensitivity of DTI parameters to the nerve regeneration process in humans *in vivo* has yet to be assessed. If we encounter sensitivity issues (for example due to the confounding effects of inflammation), we will investigate a multi-parametric approach that includes magnetization transfer ratio (MTR) MRI as a secondary measure. MTR imaging is based upon interactions between hydrogen protons on water molecules, from which the conventional MRI signal is derived, and hydrogen protons associated with solid-like macromolecules (e.g., myelin lipids), which are typically MRI-silent. Previous studies have indicated that i) MTR relates to myelin content changes in peripheral nerves (from either demyelination and/or axonal degeneration/regeneration)⁶⁶ and ii) high-resolution MTR maps of the median and ulnar can be readily acquired within clinical feasible scan times⁶⁷. We have previous experience with this technique and have demonstrated that MTR measurements of the proximal nerves of the leg correlate with functional deficits in both demyelinating/dysmyelinating and axonal inherited neuropathies⁶⁸.

[figure not shown]

FIG 14. High-resolution MTR maps of the sciatic nerve (zoomed inset) in a control subject and patient with Charcot-Marie-Tooth Type 1A (CMT1A), which is a dysmyelinating inherited neuropathy (left). MTR values in the proximal sciatic nerve correlate with clinical measures of disability (via the CMT Neuropathy score) in both demyelinating/dysmyelinating and axonal inherited neuropathies (right).

SUMMARY

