Although nerve transfers can reduce the length of axonal growth required⁵, failures still occur and revisions are rarely an option due to the aforementioned delays in detection. Current neurodiagnostics [e.g., electromyography (EMG), nerve conduction studies (NCS)] are of limited utility in severely damaged nerves, providing an incomplete picture of nerve microstructural features until target reinnervation occurs^{2, 3, 6}. Thus, physicians are limited to a “wait and watch” approach based on qualitative measures obtained from patient history and/or physical exam. This leads to a suboptimal management of peripheral nerve injuries, which in turn can lead to increased instances of irreversible muscle atrophy, paralysis, and/or formation of painful traumatic neuromas⁷.

In terms of the military, extremity injuries accounted for 54% of combat wounds in Operation Iraqi Freedom and Operation Enduring Freedom^{8, 9} and recent review of service member injuries during Operation Enduring Freedom noted significant increases in brachial plexus, ulnar, and radial nerve injuries attributable to modern warfare^{2, 10-12}. In addition, symptomatic neuroma occurs in 13% to 32% of amputees, causing pain and limiting or preventing the use of prosthetic devices^{2, 3, 6}. Take the example of a wounded warrior with a shrapnel injury to his/her elbow, resulting in the loss of an ulnar nerve segment. Even if nerve grafting is performed, true recovery (motor and/or sensory innervation of the hand) could take up to a year under typical circumstances. If the repair fails, which occurs in up to 40% of patients^{2, 3, 6}, the failure is typically not truly recognized until that year expires using current management protocols. By that time, revisional surgery is typically not a viable option due to the aforementioned onset of irreversible muscle atrophy.

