Translation of DTI techniques into human peripheral nerve has lagged developments in animals due, in part, to the technical demands of performing nerve DTI in humans (e.g., the need for high resolution data in clinically feasible scan times). Over the past decade, however, a number of technical developments (i.e., multi-element receive coils, higher field strength clinical systems) have led a number of groups to investigate the feasibility of performing DTI in human peripheral nerves *in vivo*. From these studies, the feasibility of performing DTI of the median nerve^{36, 37}, ulnar nerve³⁸, tibial and peroneal nerves³⁹, and brachial plexus⁴⁰ has been demonstrated. With feasibility demonstrated, more recent DTI studies of human peripheral nerve have focused on optimization⁴¹⁻⁴⁵ and applications in various neuropathies. Together, these results suggest that DTI metrics can be robustly measured in the distal nerves of the forearm and wrist and are quite sensitive to a number of pathologies (CIDP, GBS, carpal tunnel, trauma)⁴⁶⁻⁵¹. In fact, recent work has shown DTI is sensitive enough to detect preclinical lesions⁵² as well as subtle differences between healthy individuals⁵³. Additionally, a recent study⁵³ found that, similar to previous animal studies²², AD reflects axon integrity and while RD (and FA) reflect myelin sheath integrity in healthy individuals. This suggests that one may be able to individually probe demyelinating and axonal features of various neuropathies with DTI. Despite this large number of peripheral nerve DTI studies in humans, only two case studies^{50, 51} have sought to use DTI to monitor nerve regeneration following trauma/surgical repair. These two studies suggest that fiber tracking can detect nerve regeneration as early as 1-2 months in humans (consistent with our preliminary data); however, additional longitudinal data is needed to evaluate the ability of DTI to track and monitor nerve recovery following surgical repair. Therefore, the studies proposed herein aim to longitudinally assess DTI in patients after surgical repair for the first time. DTI measurements will then be compared to currently used electrodiagnostic measurements to determine if DTI can predict failures earlier than current techniques.

Preliminary Findings

We have explored the use of DTI as a modality to assess nerve injury of varied severity, in both ex-vivo and in vivo animal models. We also have preliminary data using DTI to assess nerve injury in humans.

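### The Aim 2 hypothesis that DTI separates failed repairs earlier than NCS/EMG has no planned analysis that could test it, and the NCS/EMG visit schedules conflict

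*Combined protocol and SAP*

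**What the plan says.** The comparative claim appears twice. The background section on DTI in peripheral nerve injury ends: "DTI measurements will then be compared to currently used electrodiagnostic measurements to determine if DTI can predict failures earlier than current techniques". Aim 2 then hypothesises that DTI can stratify "patients that are recovering versus patients with failed repair at earlier times points than nerve conduction and EMG".

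For patients, the Statistics section lists two analyses: prediction of failed recovery by DTI at each time point, with the 12-month evaluation as truth, and a plan to "evaluate correlations between the DTI parameters and EMG/NCS results". The detail matches that list. Failed and successful groups are compared on DTI parameters, and "ROC analysis will be performed to evaluate the diagnostic potential of each normalized DTI parameter at each time point and nerve segment". NCS/EMG appears only here: "to evaluate relationships between DTI parameters and NCS/EMG data (e.g., CMAP), pairwise Pearson correlations and Bonferroni corrected significance values will be calculated".

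The NCS/EMG schedule is given in three ways:
- Aim 2 text: 3, 6 and 12 months, subject to clinical indication.
- Figure 13 caption: 3, 6 and 12 months, with no condition.
- Investigational Procedure: 1, 3, 6 and possibly 12 months, with no further EMG once a patient has fully recovered clinically.

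DTI is scheduled at 1, 3, 6 and 12 months.

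**The concern.** A hypothesis that one test is earlier than another needs three things: both tests judged against the same outcome, in the same patients, and a rule for when each has separated the groups. The plan has none of these for NCS/EMG. It names no NCS or EMG measure to be classified, no ROC for either, no paired comparison and no threshold.

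At the end of the trial the claim would therefore be left unanswered or settled by an improvised rule. The obvious improvisation is to list the first visit at which each test is significant. Under the Aim 2 schedule that reading tilts toward DTI, because DTI alone has a 1-month measurement. NCS/EMG data may also be missing in ways linked to outcome, through clinical indication or through stopping EMG after full recovery.

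**Working it through.** **1. The plan's own figure.** Sample size takes failed-group FA 0.5 and SD 0.04, and states: "A conservative goal is to detect a 10% increase in FA from this decreased value to stratify successful from unsuccessful surgical interventions". The difference is 0.10 × 0.5 = 0.05, so d = 0.05/0.04 = 1.25. For a pooled two-sided t-test at 0.05 with 10 failures and 14 successes, the noncentrality is 0.05/(0.04 × √(1/10 + 1/14)) = 3.02 and power is 0.82. Equal groups give 0.80 at 11+11 and 0.83 at 12+12. The 24 patients at power 0.8 reproduce, but for one DTI difference only. NCS/EMG plays no part in the calculation.

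**2. DTI accuracy implied by these inputs.** With normal scores, AUC = Φ(d/√2) = Φ(0.884) = 0.81 for raw FA. The planned analysis variable is different: "The percent difference in DTI parameters between injured and non-injured arms will be used in all analyses to control for confounding factors". With the uninjured arm at 0.7 and SD 0.04 throughout, AUC is 0.76 if the arms are independent and 0.84 if they correlate 0.5.

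**3. Why correlation cannot answer the question.** Let p = 14/24, q = 10/24 (pq = 0.243) and within-group correlation ρ = 0.3 (assumed). The pooled correlation is (ρ + pq·d₁d₂)/√[(1 + pq·d₁²)(1 + pq·d₂²)]. If one test has AUC 0.81 (d = 1.25) and the other 0.50 (d = 0), this is 0.3/√1.380 = 0.26. Exchanging the two tests leaves it at 0.26.

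**4. Effect of the schedule on an informal reading.** The documents give no NCS accuracy, so these are assumptions: both tests equally accurate at every visit, 14 successes and 10 failures, within-group correlation between tests 0 to 0.6, between-visit correlation 0.5, significance when the 95% DeLong interval lies above 0.5, and 10,000 simulated trials. DTI is done at 1, 3 and 6 months.

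| AUC of both tests | DTI first, NCS at 3 and 6 only | DTI first, NCS also at 1 |
|---|---|---|
| rising 0.6, 0.7, 0.8 | about 33-40% | about 25-36% |
| 0.70 throughout | 54-58% | 24-34% |
| 0.81 throughout | 86% | 10-14% |

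In the rising case without 1-month NCS, NCS is first in about 20-28%. The lower two rows require NCS to be accurate already at 1 month.

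**5. What 24 patients can show in a paired comparison.** One visit, DTI AUC 0.81, all 24 tested, paired DeLong test, within-group correlation 0 to 0.6:

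| NCS AUC (assumed) | Power, uncorrected | Power, Bonferroni over 2 visits |
|---|---|---|
| 0.5 | 0.53-0.81 | 0.43-0.71 |
| 0.6 | 0.30-0.50 | 0.22-0.38 |
| 0.7 | 0.12-0.18 | 0.08-0.10 |

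The 95% CI half-width for the AUC difference is 0.20-0.30. At DTI AUC 0.76 the uncorrected powers fall to 0.38-0.64, 0.19-0.30 and 0.07-0.08.

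**6. A timing rule with a paired condition.** Suppose earlier is claimed only when DTI separates the groups at a shared visit before NCS does and the paired difference there is above 0, both Bonferroni-corrected. With one comparator, the false-claim rate for equal tests is 0.4-2.5%, against 12-34% for the first significant visit alone. If NCS is 0.5 at the first of two visits and 0.81 at the second, a true DTI lead is found in 40-60% of trials.

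**The case against.** The strongest case against is one of weight. Formal Aim 2 asks whether DTI predicts recovery, and the planned group tests and ROC analysis address that. The first-significant-visit reading is not a planned analysis, so its bias is hypothetical. A head-to-head test in 24 patients is weak, and withdrawing the claim would be enough. All of this stands. It is why the comparison should be labelled exploratory and why withdrawal is offered as the minimum repair. It does not justify leaving a stated hypothesis without a test.

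A reader might infer from the 86% row that the schedule decides the answer for DTI. The documents do not support that. The figure needs NCS at AUC 0.81 by 1 month, whereas Significance says current neurodiagnostics "are of limited utility in severely damaged nerves, providing an incomplete picture of nerve microstructural features until target reinnervation occurs". The rising case is more plausible, and its tilt is modest. A reader might also infer that stopping EMG after full recovery seriously biases the comparison. If 1 or 2 of 14 successes are skipped, the bias is 0.00 to +0.02 in AUC. The larger unknown is how many patients are never tested because testing was not clinically indicated, and the documents give no figure for that.

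Three further objections shape the repair:
- The hypothesis names EMG as well as conduction studies. Significance says needle EMG can show reinnervation at 6 to 8 weeks in some severe incomplete injuries, so an amplitude-only comparator would be incomplete.
- DTI is normalised to the uninjured arm, while NCS/EMG testing is limited to the injured nerve. If nuisance between-patient SD is 0.5 to 1 times the within-group SD (assumed), an NCS AUC of 0.81 falls to 0.79-0.73.
- Subject recruitment sets 24 as the target for mixed injuries, and Previous Experience can be read as 24 per cohort. The half-widths above need 24 patients in one analysis set; a nerve-type group of 10 gives 0.35-0.49.

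**Conclusion.** The point holds. Followed as written, the plan can address whether DTI predicts recovery but cannot test whether it does so earlier than NCS/EMG. That conclusion rests on the text alone. The schedule conflict is also textual, and it falls at 1 month, where it bears directly on the hypothesis.

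The numerical sizes are illustrations. They depend on assumed NCS accuracy, normal scores, assumed correlations and the planned 14:10 split. They support a tilt toward DTI under one of the two visit lists, not a predetermined result. They also show that a paired comparison would be informative only if NCS/EMG is close to uninformative early on. The sample-size calculation is not in dispute. Table 1 appears damaged in the available text, so nothing here rests on it.

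**What to change.** Add to Statistics, labelled exploratory because the sample size covers DTI alone:

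1. At each visit before 12 months where both tests were done, and in the same patients, report the failed-versus-successful AUC for one pre-named DTI measure and segment, one pre-named NCS measure and one pre-named EMG measure. Give each paired AUC difference with a 95% CI. State whether nerve types are pooled or analysed separately. Note that NCS/EMG is not adjusted for the uninjured arm, and show raw injured-nerve DTI as a sensitivity analysis.
2. Claim earlier only from shared visits, and only when DTI separates the groups at a visit before the comparator does and the paired difference there is above 0, with multiplicity correction. Limit the claim to the comparator analysed (NCS, EMG or both). DTI-only visits do not count.
3. Tabulate NCS/EMG not done by visit, reason (not clinically indicated, full recovery, other) and 12-month outcome. If too few patients have both tests, state that the hypothesis was not tested.
4. Fix the 12-month failed/successful definition before analysis, and keep DTI and NCS/EMG out of it for this comparison.
5. Reconcile the NCS/EMG visits and conditions in Aim 2, the Figure 13 caption and Investigational Procedure.

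If the comparison is not wanted, the minimum repair is to state in the background and in Aim 2 that earlier than NCS/EMG will not be tested, and to do step 5.

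The cost is SAP wording, a written outcome definition, a few lines of code and one data field for why a test was not done. The analysis itself asks for no scans or electrodiagnostic studies beyond those already listed. The downside is that the result may well be inconclusive.
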